Trained and approved staff at CSRL will have access to COMPASS Analytic Database to record responses and avoid storing patient level-data in a database outside of the primary COMPASS database.

Sheps Center Data Security

The Sheps Center will be housing administrative claims data and the server to which EMSPIC and CSRL will post their shared files. Claims data files at the Sheps Center are placed on a secure dataset server configured specifically to handle large-scale health utilization data. Each data file has access restricted to those users authorized by the relevant DUA. The primary dataset directories on the dataset server provide one inventory of our current claims data files. Disk-to-disk backups of claims data files on our dedicated dataset server are made nightly to two separate backup servers at two different Data Center locations on the UNC campus.

Claims data files are housed on a dedicated secure dataset server configured specifically for sensitive health utilization data. The server is physically located in a Tier II data center at [name] as part of the UNC campus. These facilities have 24x7 surveillance, multiple power sources and backup power sources, climate control, etc. Our systems administrators get access via electronic pass cards. Each card entry gets recorded with time/date stamps in facility access logs. The dataset server is behind a firewall, accessible only to Sheps Center IP addresses and UNC Secure VPN addresses. There is no printer attached to the dataset server. Only aggregated (anonymized) data and SAS output are taken off the server and onto local computers.

The server is a Linux (RedHat enterprise) server with all unneeded services disabled. Access to the claims data on the Sheps Dataset Server will be restricted to users authorized by the PI. The server is routinely patched with system updates and receives twice-weekly vulnerability scans using Qualys. Identified vulnerabilities are addressed according to UNC Security Policy. Access to the server is via SSH. Off campus access is restricted to UNC VPN connections requiring a user to authenticate with VPN before server login. VPN also provides an encrypted tunnel. SAS and Stata are typical data programs used.

The Sheps Center makes two daily disk-to-disk backups of the secure dataset server. One backup goes to a dedicated backup server within the same Tier II data center at [name]. The second goes to a second dedicated backup server at a second Tier II data center located across town at [name]. The backup data travel via an SSH tunnel over the same VLAN within the UNC campus firewalls. Both backup servers are behind a firewall denying the ability of other computers or servers to initiate a connection to the backup servers. Instead, the backup servers reach out to the secure dataset server and "pull" the backup data over.

The hard drives and CDs on which data have been delivered will be stored in a locked cabinet at the Sheps Center. Only authorized staff will have keys to the cabinet. The office will be locked when not occupied. In addition, the Sheps Center is locked 24 hours a day.

User level access to claims data files is restricted based on authorized roles. Unix groups are leveraged to provide layered controls. Users may access the data in the following ways:

- Using a computer that is on the UNC Active Directory domain and is managed by UNC ITS security tools that
 perform required scans for viruses and malware and force updated software and operating system patches. Users
 with this type of computer (desktop or laptop) can access the server directly from campus or via a remote VPN
 using SSH.
- 2. Using a computer not managed by UNC ITS security tools via a specifically designated secured UNC Virtual Computer (virtual computing lab), which connects to the server. This virtual desktop is setup, maintained, and managed by Sheps Center sys admins. At the end of a working session, the virtual computer is destroyed along with any data that may have been used locally in the virtual computer instance.

Logical access is safeguarded at multiple levels:

1. The claims data files will be housed on a dedicated secure dataset server configured specifically for sensitive health utilization data. The server is physically located in a Tier II data center at [name],

Application - IRB00035998

an extension of the UNC campus. These facilities are governed by the UNC ITS Data Center Operations policies and procedures. They have 24x7 surveillance, required visitor sign-in with escorts, multiple power sources and backup power sources, climate control, etc. Our systems administrators get access via electronic pass cards. Each card entry gets recorded with time/date stamps in facility access logs. While other sys admins of ITS have access to the same physical space where our server racks are housed, these are trusted people governed by central campus ITS policies and procedures. Also, the Data Center space has logged entry of individuals and is under constant surveillance where any unauthorized physical access would be monitored and recorded. Significant sanctions are known and apply, up to and including job termination and possible criminal prosecution.

- 2. The designated server is firewalled allowing only SSH port 22 to be open. All unnecessary ports are closed and all unnecessary services are disabled. User level access to files is restricted based on authorized roles. SSH connections are limited to UNC subnets and UNC VPN addresses. Access to the designated secure dataset server is restricted to computers within the UNC network domain. Connections originating outside the UNC network are restricted to UNC VPN authentication first and then system-level user/pw authentication. Users may only connect using SSH and Kerberos authentication leveraging the UNC Single Sign-on policies and procedures.
- 3. Nightly secure backups are performed to two dedicated backup servers one backup within the same data center within the firewalled subnet and the second backup in another data center across town via the same VLAN. The original CMS data is not backed up to tape but instead the delivery media is kept for backup, if needed. In case of (a) data center disaster, or (b) backup failure, a second backup computer is housed in a second campus data center. Two system administrator computers are allowed to connect to backup servers to control them. Firewall prevents all other computers from reaching backup servers. Backup computers initiate the network connections to the server. It is not possible for any user to initiate a connection to a backup server from the main server or from any other computer except for those owned by two system administrators. All network connections are encrypted.
- 4. The designated server is kept up-to-date with recommended operating system patches and patches for applications. The server is scanned twice weekly for vulnerabilities using the UNC licensed QualysGuard SaaS software. System administrators monitor event logs, security logs, and system logs. UNC uses Snort for intrusion detection and Tipping Point for intrusion prevention. These systems/appliances are monitored and handled centrally by the UNC ITS Security Office. Suspicious activity is reported to the Sheps Center's Security Liaison for investigation and handling with assistance from the central ITS Security Office. If these data will be delivered via CD or hard drive, the media will be kept in a locked storage location provided by the project, with key access only to research team members.
- 5. Project staff at the Sheps Center will access the secure dataset server via SSH using computers physically in the Sheps Center Building. The Sheps Center Building's exterior doors are locked 24x7. Individual offices inside the Sheps Center are also locked. Staff enter using an authorized key. Visitors must be buzzed in using a video intercom system and then must report to the receptionist and sign in. There are no servers physically located in the Sheps Center Building.

Description of the Secure Data Transfers

Secure Data Transfer between the COMPASS DB and eCare Plan Informatics (eCPI) DB

Data transfer between the COMPASS Database and the eCPI Database will be via RESTful web services designed specifically for the limited datasets being exchanged. Secure data transfer protocols will be in place to provide fully encrypted transmissions. The eCare Application may retrieve and update patient data from the COMPASS Database (the database of record for patient data) for use during a patient visit in order to foster the use of that data in creating an eCare Plan. Patient data is requested based on key identifiers and the resulting match reflected in the eCare application. The web service will allow for the transmission of data stored in the eCPI database to the COMPASS Database for use in analysis as well as patient status updates and notifications to appropriate study personnel. The eCare database remains the database of record for those intervention data while making the COMPASS DB and associated application aware of the analytical data needed for the study. The eCare application will contain the logic necessary during the flow of its data collection to validate data with the patient as well as prevent implausible and/or out-of-range responses.

Application - IRB00035998

Secure Data Transfer between COMPASS DB and CSRL

As described above, to facilitate surveys, patient and caregiver names, phone numbers and addresses, date of hospital discharge, preferred day and time of contact, as well as PAC information will be exported as a CSV file from the Analytic Database. This file will be stored on a secure server (\ceil.schsr.unc.edu) and accessed by staff at CSRL for pre-loading into their phone system once per week.

Data Access for Analysis

We have in place secure operations for sharing SAS datasets between investigators to ensure safety and confidentiality of patients. Datasets will be stored on a secure server that is accessed through a virtual network. Study investigators will be granted access to this server for running data reports and analyses of the study data. These internal datasets will contain the COMPASS Unique participant IDs to link data in different files together. PHI (including date of birth, medical record number, names, addresses, phone numbers, and email addresses) will be removed from datasets prior to export of these SAS datasets from the COMPASS Database. Data sharing with investigators outside of UNC will occur through data transfers using secure File Transfer Protocols.

REDCap (Research Electronic Data Capture)

COMPASS Study will use REDCap at Wake Forest Baptist Medical Center to store responses from hospital stakeholders and track stakeholder engagement activities.

Vanderbilt University, with collaboration from a consortium of institutional partners, has developed a software toolset and workflow methodology for electronic collection and management of research and clinical trial data. REDCap (Research Electronic Data Capture) is hosted at Wake Forest Baptist Medical Center through the Biomedical Informatics program of the Translational Science Institute. REDCap servers are located within the Wake Forest Baptist Health firewall and all web-based information transmission is SSL (Secure Socket Layer) encrypted; the databases are backed up nightly through the institution's enterprise backup system. Users are granted access to the system using their unique medical center username and password with specific access rights setup for each study. REDCap was developed specifically around HIPAA-Security guidelines and is used by 1,000+ academic/non-profit consortium partners on six continents with over 195,000 research end-users (www.project-redcap.org).

Application - IRB00035998

Data and Safety Monitoring

The COMPASS Data and Safety Monitoring Board (DSMB) will serve to support as an independent review board of the study and study activities to protect patients. Adverse events among this patient population are likely; however because COMPASS is a minimal/no risk study, COMPASS will not be tracking adverse events. Therefore the COMPASS DSMB will provide thrice-annual review of study activities providing external review and assurance on the performance of the study. This thrice-annual review will include case ascertainment and enrollment; expected versus observed outcomes; review of percentage of participants in the intervention receiving the 2-day call, the 7-14 day visit, the eCare Plan; and review of protocol deviations.

To avoid any appearance of conflict of interest, it is critical that DSMB members not be involved in the study, have no vested interest in its outcome, have no ties to the study investigators (e.g., not from the same institution and no history of extensive collaboration), and have no financial ties to any commercial concerns likely to be affected by the study's outcome. If at any time a DSMB member perceives that he/she or another member of the Board has a potential conflict of interest, he/she is obligated to bring the issue to the attention of the full DSMB for open discussion and resolution.

Responsibilities

- 1. COMPASS DSMB members will be responsible for assuring study participants are not exposed to unnecessary, unreasonable or unexpected risk, and is charged with ensuring that the study is conducted according to the highest scientific and ethical standards.
- 2. Specifically, oversight will include the following areas:
 - Review of the COMPASS Manual of Operations and Procedures (MOP), the analysis plan, and implementation of the study procedures at the first DSMB meeting.
 - Review of study protocol including our informed consent processes.
 - The DSMB may recommend modifications or request clarifications of the protocol.
 - Review of the study outcomes and their clear definition, study procedures, informed consent documents, data security, and investigator responsibilities.
 - In subsequent meetings, the DSMB will focus on case ascertainment and enrollment; expected versus observed outcomes; review of percentage of participants in the intervention receiving the 2-day call, the 7-14 day visit, the eCare Plan; and review of protocol deviations.
 - Any other areas the DSMB considers oversight to be necessary.

Frequency of Meetings and Communication between DSMB and COMPASS

COMPASS DSMB members will meet annually. The first meeting will take place in person, in early 2016. Subsequent meetings will take place remotely over webinar. Meetings will be closed to the public. Only DSMB members and members of the COMPASS Executive Leadership Committee will attend. ELC members will prepare in advance a DSMB report for review (Appendix 32). Each meeting will start with discussion between COMPASS Executive Leadership Team and DSMB and then the DSMB will meet privately without study personnel.

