At 90 Days, stroke survivors will receive a phone call from the Carolina Survey Research Lab (CSRL). CSRL will follow a telephone script which includes consent (Appendix 10) and conduct blinded assessments (Appendix 23 and 24). If the patient prefers s/he can request that a proxy answer questions and provide verbal consent and HIPAA Authorization on her/his behalf. In the event contact is never made with the patient by phone or connection is lost (e.g. the number is not in service, no one answers the phone calls, call is answered but is disconnected prior to the researcher sharing the reason for calling, or there is loss of connection during the call) we will mail an abbreviated version of the survey with a letter explaining the survey purpose (Attachment 25). We will also include a self-addressed envelope with prepaid postage to the patient to gather responses via paper survey. This abbreviated survey contains the SIS-16, global health rating scale and blood pressure questions.

Approximately one year later the study will acquire claims data from Medicare, Medicaid, State Insurance Plan, and Blue Cross Blue Shield. We plan to use a HIPAA Waiver to acquire the data sets and along with this application we are asking for a waiver of signed consent to link all enrolled patients to the claims data sets.

Phase 1: Patients in COMPASS-Intervention Hospitals

In addition to the activities outlined in the Control Hospitals section above, patients who enter the study through a COMPASS Intervention hospital will receive: (1) a follow-up phone call 2 days after being discharged from the hospital, (2) a 7-14 day Advanced Practice Provider visit, (3) a follow-up 30 day phone call, and (4) a follow-up 60 day phone call. The structure and processes of this COMPASS intervention are consistent with the Center for Medicare and Medicaid (CMS) Transitional Care Management Codes. In essence the COMPASS study is an evaluation of the implementation of CMS recommendations for post hospital care coordination.

The process for determining Eligibility for COMPASS patients is identical to that of Control patients.

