Secondary Outcome	Cognition	MOntreal Cognitive Assessment (MOCA) Mini	@90 days, consenting patients asked by CSRL	24
Secondary Outcome	Medication Adherence	4-item Morisky Green-Levine Scale	@90 days, consenting patients asked by CSRL	24
Secondary Outcome	Secondary Prevention Self-Monitoring of BP	By asking: "Do you check your blood pressure at home?"	@90 days, consenting patients asked by CSRL	24
Secondary Outcome	Blood Pressure Management Effectiveness	For those who check BP at home, we ask: "Is your blood pressure less than 140/90 most of the time?"	@90 days, consenting patients asked by CSRL	24
Secondary Outcome	Falls and Hospitalization*	Questions to capture: Number of falls, injuries, and hospitalizations *Note: Note: Outcome is binary variable of Fall either Yes or No. Hospitalizations, injuries and number of falls were collected but were not used in the analyses	@90 days, consenting patients asked by CSRL	24

Secondary Outcome	Fatigue	PROMIS Fatigue Instrument – Adult Short Form 4A	@90 days, consenting patients asked by CSRL	24
Secondary Outcome	Satisfaction with care	Questions on how the patient felt about care and treatment from health care providers.	@90 days, consenting patients asked by CSRL	24
Exploratory Aim	Use of Community Resources	By asking: "Since discharge from the hospital, have you used services such as Senior Services, Meals on Wheels, in-home aides, or stroke survivor or caregiver support groups?"	@90 days, consenting patients asked by CSRL	24
Data collected to support the operations of the trial.	Initial Presentation Data	Hospital arrival and Mode of arrival, Ambulatory status prior to admission, Diagnosis at admission, NIHSS, Imaging performed, etc.	Entered into the COMPASS Database by the hospital	9
Data collected to support the operations of the trial.	Demographic Data	DOB, Race, Gender, Insurance, Medical History, Medication, etc.	Entered into the COMPASS Database by the hospital	9
Data collected to support the operations of the trial.	t-PA Data	Time t-PA was initiated, BP and Glucose levels, bleeding complications, etc.	Entered into the COMPASS Database by the hospital	9
Data collected to support the operations of the trial.	In-hospital Data	Admission data, secondary prevention counseling, treatment, lipid profile, medications, treatments, etc.	Entered into the COMPASS Database by the hospital	9

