BPVALsys	Enter number between 50 and 250. (GO TO BPVALdia) 8=DON'T KNOW(GO TO PCP) 9=REFUSE(GO TO PCP)	What was the value of your/his/her last blood pressure? Please provide the systolic (top number) and diastolic (bottom number). IN: ENTER TOP NUMBER HERE AND BOTTOM NUMBER ON FOLLOWING SCREEN. IF NEEDED: We are interested in your most recent BP no matter who took the measurement.	
BPVALdia	Enter number between 35 and 135. (GO TO BPWHO)	What was the value of your/his/her last blood pressure? Please provide the systolic (top number) and diastolic (bottom number). IN: ENTER BOTTOM NUMBER HERE	
ВРЖНО	1=you/the patient himself/the patient herself 2= a healthcare professional 3= a family member, or 4= someone else? (GO TO BPWHO_OTHER)	Was this blood pressure measurement taken by	
BPWHO_OTHER	OPEN TEXT (50 CHARACTERS)	Who took the blood pressure?	
PCP	0=NO (GO TO PTVIS) 1=YES (GO TO PCPVIS) 8=DON'T KNOW (GO TO PTVIS) 9=REFUSE (GO TO PTVIS)	Is there a particular doctor's office, health center, or other place that you/he/she usually go/goes if you/he/she are/is sick and	

Application - IKB00035998	T		
		need/needs advice about your/his/her health?	
		IN: THIS COULD INCLUDE ANY TYPE OF DOCTOR IF THE RESPONDENT USES THEM REGULARLY. IT DOES NOT INCLUDE A HOSPITAL EMERGENCY DEPARTMENT.	
PCPvis	0=NO (GO TO PTVIS) 1=YES(GO TO PTVIS) 8=DON'T KNOW(GO TO PTVIS) 9=REFUSE(GO TO PTVIS)	Have/Has you/he/she visited a doctor or nurse from that office, health center or other place since you/he/she were/was discharged from the hospital after your/his/her stroke?	
PTvis	0=NO (GO TO OTvis) 1=YES (GO TO PTvisL) 8=DON'T KNOW (GO TO OTvis) 9=REFUSED (GO TO OTvis)	Since you/he/she were/was discharged home on [PRELOAD DISCHARGE OR NEW_DISCHARGE, IF FILLED] after your/his/her stroke or TIA, have/has you/he/she received any services from a physical therapist? IF NEEDED: Physical therapists help patients with their mobility, (for example, walking, moving from sitting to standing, going up stairs, getting in and out of bed) and physical activity.	
PTvisL	1=your/his/her home (GO TO OTvis) 2=an outpatient clinic, or (GO TO OTvis) 3=both? (GO TO OTvis) 8=DON'T KNOW (GO TO OTvis) 9=REFUSED (GO TO OTvis)	Did you/he/she receive the services in	

Application - IKB000.			

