Application - IRB00035998		1	
	8=DON'T KNOW (GO TO PROMIS_INTRO) 9=REFUSE (GO TO PROMIS_INTRO)	hospital overnight for any reason? IN NOTE: WE ARE	
		INTERESTED IN NUMBER OF ADMISSIONS, NOT NIGHTS	
PROMIS_INTRO		The next few questions are about feelings of tiredness or fatigue	PROGRAMMING: SKIP IF PROXY=1 OR 2
PROMIS1	1=Not at all 2=A little bit 3=Somewhat 4=Quite a bit 5=Very much 8=DON'T KNOW 9=REFUSE	During the past 7 days, how often have you felt tired or fatigued? Would you say	PROGRAMMING: SKIP IF PROXY=1 OR 2
PROMIS2	1=Not at all 2=A little bit 3=Somewhat 4=Quite a bit 5=Very much 8=DON'T KNOW 9=REFUSE	During the past 7 days, how often have you had trouble starting things because you were tired? Would you say	PROGRAMMING: SKIP IF PROXY=1 OR 2
PROMIS3	1=NOT AT ALL 2=A LITTLE BIT 3=SOMEWHAT 4=QUITE A BIT 5=VERY MUCH 8=DON'T KNOW 9=REFUSE	(In the past 7 days,) how run-down did you feel on average? (Would you say)	PROGRAMMING: SKIP IF PROXY=1 OR 2
PROMIS4	1=NOT AT ALL 2=A LITTLE BIT 3=SOMEWHAT 4=QUITE A BIT 5=VERY MUCH 8=DON'T KNOW 9=REFUSE	(In the past 7 days,) how fatigued were you on average? (Would you say)	PROGRAMMING: SKIP IF PROXY=1 OR 2
SATIS_INTRO		The next several questions are about the care you've/he's/she's received from your/his/her physicians, nurses and other health care providers since you/he/she had your/his/her stroke or TIA.	

rippiication ittboo			
Satis1	1=Never 2=Sometimes 3=Usually 4=Always 8=DON'T KNOW 9=REFUSE	Thinking about the care you/he/she have/has received for your/his/her stroke or TIA recovery since you/he/she were/was discharged from the hospital on [PRELOAD DISCHARGE DATE], how often did your/his/her physicians, nurses and other health care providers Explain things in a way that was easy [for him/her] to understand? Would you say INTERVIEWER NOTE: PATIENTS SHOULD THINK ABOUT THE CARE THEY'VE RECEIVED FROM ALL OF THEIR PHYSICIANS (E.G., SPECIALIST AND	
Satis2	1=Never 2=Sometimes 3=Usually 4=Always 8=DON'T KNOW 9=REFUSE	PRIMARY CARE PROVIDERS) (Thinking about the health care providers you/he/she have/has seen since you/he/she were/was discharged from the hospital) How often did these providers listen carefully to you/him/her? Would you say	
Satis3	1=NEVER 2=SOMETIMES 3=USUALLY 4=ALWAYS 8=DON'T KNOW 9=REFUSE	(Thinking about the health care providers you/he/she have/has seen since you/he/she were/was discharged from the hospital) How often did they seem to know the important	

Application - IRB00035998		

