ComRes5	0=NO 1=YES 8=DON'T KNOW 9=REFUSE	(Since discharge from the hospital after your/his/her stroke) How about exercise classes that are open to the general public, like ones offered at a church or fitness center?	
ComRes6	0=NO 1=YES 2=DOES NOT SMOKE 8=DON'T KNOW 9=REFUSE	(Since discharge from the hospital after your/his/her stroke, how about) programs to help you quit smoking?	
ComRes7	0=NO 1=YES 8=DON'T KNOW 9=REFUSE	(Since discharge from the hospital after your/his/her stroke, how about) a falls prevention program that teaches you how to improve your balance and strength so you don't fall?	
ComRes8	0=NO 1=YES 8=DON'T KNOW 9=REFUSE	(Since discharge from the hospital after your/his/her stroke, how about) programs that provide meals – either delivered to your house or a central location like a church or community center?	
ComRes9	0=NO 1=YES 8=DON'T KNOW 9=REFUSE	(Since discharge from the hospital after your/his/her stroke, how about) a support group for stroke survivors? IN NOTE: these are groups that provide social support, information, and resources for stroke survivors	
ComRes10	0=NO 1=YES	(Since discharge from the hospital after your/his/her stroke, how about)	

Application - IRB00035998			
	8=DON'T KNOW 9=REFUSE	medication assistance or management services to help pay for the medications or to help understand and manage the medications? IN NOTE: management services are usually offered by pharmacists.	
ComRes11	0=NO 1=YES 8=DON'T KNOW 9=REFUSE	(Since discharge from the hospital after your/his/her stroke, how about) transportation services to get you to your healthcare appointments or community activities? IN NOTE: THIS DOES NOT INCLUDE REGULAR PUBLIC	
ComRes12	0=NO 1=YES 8=DON'T KNOW 9=REFUSE	TRANSPORTATION (Since discharge from the hospital after your/his/her stroke, how about) support services for your family or caregivers? IN NOTE: these are groups or services that provide social support, information, and resources for caregivers/family members of storke survivors?	
ComRes13	0=NO (GO TO EDUC) 1=YES (GO TO COMRES14) 8=DON'T KNOW (GO TO EDUC) 9=REFUSE (GO TO EDUC)	Are there any other services you've/he's/she's used that I haven't mentioned?	
ComRes14	SPECIFY OTHER OPEN TEXT [250 CHAR]	What are those?	

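### The satisfaction-with-care items cannot record that no provider was seen, so a difference in contact between the arms can pass for a difference in satisfaction

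*Protocol*

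**What the plan says.** The patient outcomes table (Protocol, Data Collection and Outcome Measures) lists satisfaction with care as a secondary outcome asked at 90 days and describes it as "Questions on how the patient felt about care and treatment from health care providers". It gives no scoring rule.

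Appendix 23 holds the items. Satis1 is coded "1=Never 2=Sometimes 3=Usually 4=Always 8=DON'T KNOW 9=REFUSE", and Satis2 to Satis6 use the same set. The paper copy in Appendix 24 offers only the four frequencies. The items take contact for granted; Satis2, for example, asks "How often did these providers listen carefully to you/him/her". The abbreviated mail survey omits these items, so the outcome comes from the telephone interview alone.

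Earlier in the interview, PCP asks whether the patient has a usual place of care. If so, PCPvis asks whether the patient has "visited a doctor or nurse from that office, health center or other place since" discharge. A 'No' to PCP goes straight to the physical therapy question, and so does every answer to PCPvis: "0=NO (GO TO PTVIS) 1=YES(GO TO PTVIS) 8=DON'T KNOW(GO TO PTVIS) 9=REFUSE(GO TO PTVIS". Neither question leads around the satisfaction items.

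On the arms, the protocol says: "In addition to the activities outlined in the Control Hospitals section above, patients who enter the study through a COMPASS Intervention hospital will receive" a 2-day call, "a 7-14 day Advanced Practice Provider visit", and calls at 30 and 60 days. The post-acute coordinator (PAC) also helps intervention patients schedule primary care and advanced practice visits. Control patients receive their hospital's own standard care.

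**The concern.** The outcome is meant to capture how patients felt about their care. For a patient with no care since discharge there is nothing to rate, yet the interviewer still asks all six items. 'Never' then enters as the worst rating of encounters that did not take place. 'Don't know' removes the patient from the comparison or leaves a value to impute.

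If such patients were equally common in both arms, this would mostly add noise. Contact, however, is what COMPASS sets out to change. The score can therefore mix whether contact occurred with how it was rated, and the two arms can differ on it even when patients who saw a provider rate their care identically. A favourable result could then be reported as better-rated care when it shows only more frequent contact. Contact already has its own endpoint: time to first ambulatory visit with any provider (SAP Section 4.4).

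**Working it through.** **No figure to reproduce.** The documents give no SD, effect size, power or scoring rule for this outcome. What follows is illustration.

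**Inputs from the protocol:** about 6,000 potentially eligible patients in Phase 1; 40 randomized units.

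**Assumptions:** 3,000 telephone responders, ICC 0.01, two-sided 5% test, items averaged on the 1 to 4 scale, mean 3.5 and SD 0.7 among patients with contact in both arms (no true difference). Let g be the no-contact share in control minus that in intervention, and p the proportion of no-contact patients who answer 'Never'.

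**Standard error.** Cluster size is 3000/40 = 75. In SD units, SE = 2 × √[(1 + 74 × 0.01)/3000] = 2 × √(1.74/3000) = 0.048.

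**Bias.** g × p × (3.5 − 1) points; divide by 0.7 for SD units.

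**False-positive rate.** Φ(bias/SE − 1.96) + Φ(−bias/SE − 1.96).

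With g = 5 percentage points:

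| p | bias, points | bias, SD | bias/SE | false-positive rate |
|---|---|---|---|---|
| 10% | 0.0125 | 0.018 | 0.37 | about 7% |
| 25% | 0.031 | 0.045 | 0.93 | about 15% |
| 50% | 0.0625 | 0.089 | 1.86 | about 46% |

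With p fixed at 50%, gaps of 2, 5 and 10 points give 12%, 46% and 96%. The answer depends heavily on both unknowns.

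**A fuller calculation** reweights for patients who drop out through 'Don't know' and widens the SD for the cluster of 1s. It assumes mean 3.6, SD 0.7, 50% to 60% response, ICC 0.01 to 0.02 and 20 clusters per arm.

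| No contact, control vs intervention | half answer 'Never' | all answer 'Never' |
|---|---|---|
| 5% vs 2% | 0.04 points; 15–20% | 0.08 points; 37–53% |
| 10% vs 5% | 0.07 points; 30–43% | 0.13 points; 66–84% |
| 15% vs 5% | 0.14 points; 79–93% | 0.26 points; 99–100% |

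**The 'Don't know' route.** If every no-contact patient is missing and resembles the rest, the bias is zero and the error rate stays at 5%. Otherwise, suppose 30% of all patients would rate care 3.2 and 70% would rate it 3.7, with 15% vs 5% missing. If 60% of the missing belong to the lower class, its share among the remaining patients is (0.30 − 0.15 × 0.6)/0.85 = 0.247 in control and (0.30 − 0.05 × 0.6)/0.95 = 0.284 in intervention. The spurious difference is −0.5 × 0.037 = −0.019 points, against COMPASS. If only 10% of the missing belong to it, the same calculation gives +0.012. The sign is not predictable, and the effect is small in this example.

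**The case against.** **The no-contact group may be small in both arms.** The items cover physicians, nurses and other providers over about 90 days. Control hospitals deliver their own post-acute care; the hospital survey (Appendix 2) lists follow-up calls and clinic visits as possible existing practice. The enrollment form records pre-scheduled follow-up visits in both arms, and intervention patients can miss theirs. A reader might infer that control patients have no contact at all. The documents show only that they have no study-scheduled contact. This narrows the gap without closing it.

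**Being unseen is arguably part of the effect.** In a pragmatic intention-to-treat trial, a control patient to whom nobody explained anything because nobody saw the patient is a consequence of allocation. That is a fair reading of the outcome, and comparing only patients with contact would itself select after randomization. It is why both versions should be shown. The present codes allow neither to be isolated.

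**The scoring rule may exist elsewhere.** The supplied SAP is the claims addendum; the Phase 1 SAP it cites was not available. That plan may settle scoring and the handling of 'Don't know', but it cannot recover an answer the interview never collected.

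**It is late.** Phase 2 enrollment was planned to end in January 2019 and the protocol is dated March 2021. A new code cannot help completed interviews, so the sensitivity analysis matters most.

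**Two further readings go too far.** A reader might infer that missing answers also favour COMPASS; only 'Never' has a predictable direction. A reader might also infer that the problem is undetectable. In fact 'Don't know' is stored separately from 'Refuse', and claims record ambulatory visits for linked patients.

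**Conclusion.** The point holds as a possible bias in one secondary outcome. The instrument gap and the difference in scheduled contact are both plain in the protocol. 'Never' answers from patients without contact push the comparison towards COMPASS; 'Don't know' answers produce selection of unknown sign. SIS-16, the primary outcome, is untouched.

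The size cannot be derived from the documents. The figures of about 15% (a quarter answering 'Never') and about 46% (half) rest on an assumed 5-point contact gap and on assumed mean, SD, responder number and ICC. They show that a modest imbalance could matter in a trial this large, not that it occurred. The documents do not support saying that the outcome will show a spurious benefit.

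**What to change.** **For any further use of the survey.** Add a code such as 'no physician, nurse or other provider seen since discharge' to Satis1 to Satis6 in Appendices 23 and 24. The survey already has a code of this kind for the smoking-program item: "0=NO 1=YES 2=DOES NOT SMOKE 8=DON'T KNOW 9=REFUSE". Do not score it as 'Never'. Report its share by arm, and show the arm comparison three ways: these patients excluded, set to the worst rating, and set to the average rating.

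**For interviews already done.**

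- Tabulate 'Don't know' and all-'Never' response patterns by arm.
- Flag patients with no recorded contact: PCP = No or PCPvis = No; and PTvis, OTvis and STvis all No; and, in the intervention arm, no completed COMPASS clinic visit or PAC call on the disposition forms (Appendices 34 and 35). PCP = No must be included because those patients never reach PCPvis. The disposition forms are needed because a patient seen only at the COMPASS clinic would otherwise be flagged as unseen.
- Check the flag in both arms against claims ambulatory visits (SAP Section 4.4) where linked, because the disposition forms exist in the intervention arm only.
- Run the same three comparisons on flagged patients as a sensitivity analysis.

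Interpret any satisfaction difference alongside the difference in contact.

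**Cost.** One response code, a short addition to the analysis plan and one sensitivity table. The outcome is then reported in two parts, and the retrospective flag is only a proxy.
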